6.2.3 Carotid and Femoral Intima-Media Thickness (IMT)

B-mode ultrasound examination will also be performed, using a 14.0 MHz multi-frequency linear array probe attached to a high resolution ultrasound machine (Vivid 7 Pro, GE Healthcare, USA). All scans are going to be performed by the same operator as previously described(30). Carotid intima-media thickness (ccIMT) will be measured at the distal 1.0 cm of the common carotid proximal to the bifurcation. In each segment 3 measurements of the maximal IMT in the far wall will be averaged, after excluding plaque thickness. The average of the maximal IMT will be used in the analyses. Femoral IMT (fIMT) will be measured on each side, scanning a 1cm-long arterial segment proximal to the femoral bifurcation, defined as the common femoral artery segment and the average value of IMT of the far wall will be estimated. A cutoff value of >0.9 mm for mean ccIMT or fIMT will be considered increased. Plaques to carotid and femoral arteries are defined as a focal structure that protrudes into the arterial lumen of at least 0.5 mm or 50% of the surrounding IMT value or demonstrates a thickness of >1.5 mm. The relative echogenicity of the atheromatous plaques and the IMT will be assessed by Artery Measurement Software (AMS), an automated piece of software for

dedicated analysis of gray scale median (GSM) (31) and carotid artery remodeling of the common carotid artery by calculating the arterial relative wall thickness (RWT) and the arterial cross-sectional are (CSA) (32).

6.2.4 Ankle Brachial Index (ABI)

The ABI is a simple, non-invasive diagnostic test for lower-extremity peripheral arterial disease (PAD) with high validity of the test for stenosis \geq 50% in leg arteries (sensitivity \approx 95% and specificity \approx 100%) (33). The ABI can be easily measured by the means of ordinary blood pressure cuff and a Doppler ultrasonic sensor. The blood pressure cuff is used to measure systolic blood pressure in the brachial artery of both arms by use of the Doppler detector in the antecubital fossa. The blood pressure cuff is then applied to the ankle, and the Doppler probe is used to determine systolic blood pressure at the left and right posterior tibial arteries and dorsalis pedis arteries. The ABI for each leg equals the ratio of the higher of the 2 systolic pressures (posterior tibial or dorsalis pedis) in the leg and the average of the right and left brachial artery pressures, unless there is a discrepancy \geq 10 mm Hg in blood pressure values between the 2 arms. An ABI <0.90 in either leg is considered evidence of PAD, and progressively lower ABI values indicate more severe obstruction. Besides an indicative marker for leg artery disease ABI has been shown to serve as a surrogate marker for atherosclerosis having at the same time predictive value future cardiovascular events, independent of established risk factors(34).

All the above mentioned vascular measurements will be performed at each time point, that is on baseline and days 1,2,8,9,15 and 16 of cycle 1 and on days 1,2 of cycle 2 and 3 before and 2 hours after drug administration. The B-Mode ultrasound of the carotid and femoral arteries will only be performed at baseline. On cycle 6 all vascular measurements will be repeated to assess the chronic effect of proteasome inhibition on vascular function and atherosclerosis. Subjects will be instructed to fast overnight, to refrain from smoking, ingesting alcohol or caffeine on the day of testing and to hold any vasoactive medications for 12 h before the imaging studies.

6.2.5 24-hour Ambulatory Blood Pressure Monitoring (ABPM)

Patients will have their blood pressure monitored for 24 hours during the 1st day of cycles 1, 2, 3 and 6.

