Objectives:	 Primary to describe cardiovascular complications associated with the use of carfilzomib and investigate the role of the UPS inhibition, in patients treated with carfilzomib and dexametahsone, on atheromatosis and vascular inflammation and function 						
	 Secondary to outline the clinical significance of carfilzomib toxicity in hemodynamic parameters and cardiovascular function and vascular structure 						
Endpoints	 Primary Changes in hemodynamic markers (peripheral and aortic office blood pressure and 24 hour ambulatory BP monitoring parameters) and in peripheral vascular function (endothelial function, arterial stiffness, arterial wave reflections) before, during and after study drug administration 						
	 Secondary Changes in subclinical atherosclerosis markers (carotid intima-media thickness and vascular wall and plaque echogenicity) changes in markers of cardiac function (ejection fraction, 						

Population:	 systolic and diastolic strain and strain rate) changes in circulating cardiac and vascular inflammatory biomarkers (NtproBNP, cTnT, C-reactive protein, interleukin 6, vascular cell and intercellular adhesion molecule-1, E-selectin, and monocyte chemoattractant protein-1) before and after study drug administration Patients with relapsed or refractory myeloma treated with carfilzomib as per approved indications
Phase:	This is an observational, non interventional, prospective study
Number of Sites:	This is a single center study
Description of Study assessments:	Patients with an indication to receive carfilzomib & dexamethasone will be treated according to approved dose and schedule
	A. Vascular studies: Vascular measurements will be performed at baseline before and after dexamethasone, before and after CFZ administration, 2 hours and 24 hours after CFZ administration. These measurements will be repeated on days 8,9,15 and 16 of cycle 1, on days 1,2 of cycles 2 and 3 and days 1,2,15 and 16 of cycle 6 or earlier if the patient develops progression of disease. Vascular measurements include assessment of arterial stiffness, arterial wave reflections, subclinical carotid and femoral atherosclerosis and carotid plaque composition, using non-invasive well-validated techniques. Blood pressure will be evaluated using 24h hour ambulatory monitoring at baseline and on days 1 and 8 of cycle 1 and at the beginning of cycles 2, 3 and 6.

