4.1 Description of the Study Design

The present study will assess patients with multiple myeloma receiving the proteasome inhibitor carfilzomib (CFZ), in order to investigate, *in vivo*, a wide spectrum of human atherosclerosis stages, cardiovascular risk factors and subclinical atherosclerosis at multiple successive stages in a human model under conditions of global UPS inhibition.

A. Investigation of the role of the UPS inhibition on vascular inflammation and atheromatosis

Circulating biomarkers of vascular inflammation (CRP, IL-6, ICAM-1) and vascular function (endothelial function, arterial wave reflections) and structure (intima media thickness, peripheral atheromatous plaques, plaque echogenicity and arterial stiffness) will be measured at baseline at pre-specified short and long-term time points after treatment. The acute response of vascular function and inflammatory markers to CFZ as well as long term changes in vascular structure after treatment will be assessed. These changes will be examined in comparison to the degree of change in UPS activity by validated techniques.

B. Outline of the clinical significance of carfilzomib therapy in hemodynamic parameters and vascular function and structure

In the same population and under the same design, changes in 24hour ambulatory blood pressure (BP) parameters as well as in vascular parameters as described above will be assessed focusing on time points with significant BP increments and vascular dysfunction. Subsequently, we will examine whether the magnitude of deterioration in these parameters of interest is associated with the degree of UPS activity.

5. Study enrollment and withdrawal

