6.5 Measurement of circulating cardiac and vascular inflammatory biomarkers

Plasma and serum samples will be obtained by venipuncture on admission and stored at - 70°C. Plasma probes will be centrifuged for 15 minutes at 10.000 g within 30 minutes of

collection. Probes will be aliquoted and stored at -70°C till analysis. The concentrations of Creactive protein, interleukin 6, vascular cell and intercellular adhesion molecule-1, E-selectin, and monocyte chemoattractant protein-1 will be measured in ethylenediaminetetraacetic acid (EDTA)-plasma at the Oncology Laboratory of the Department of Clinical Therapeutics wellcharacterized enzyme immunoassays. N-terminal pro-B-type natriuretic peptide will be measured with a sandwich immunoassay on an Elecsys 2010 instrument (Roche Diagnostics). Serum cardiac troponin T concentrations will be measured using statndard procedures.

7. Timelines of the study

Vascular measurements and blood collection will be performed at baseline before and 2 hours after dexamethasone and carfilzomib administration. These measurements will be repeated as shown below:

	Before Dexa	After Dexa	Before & after CarD	After CarD	Before & after CarD								
Time points	d -2		d0	d2	d8	d9	d15	d16	C2d1	d2	C3d1	d2	C6d1or 6 months after baseline
Vascular studies	x	X	X†	X	Xt	X	Xt	X	Xt	X	Xt	x	t x
24h ambuatory BF monitoring	×		X*		Х*				X*		X*		X*
Cardiac US	X					1				. 8			X**
Blood for Proteasome activity			x	x	x	x	X?	x	x	x			Xt
Serum collection for cardiac biomarkers	×		×t		×t		×t		×t		x		x

Schedule of assessments

* During 24th of CarD

**Only before C6d1

†2 measurements/ samples at this day

The subjects will be evaluated for AE at all visits.

8. Data presentation and statistical analysis

Data will be presented as mean ± standard deviation (SD). Continuous variables will be tested for normal distribution with the Kolmogorov-Smirnov test. Repeated measures ANOVA will be performed in order to assess significant variations of parameters of interest over time. Linear mixed models analysis will be performed in order to adjust for possible confounders over time. All tests will be two-tailed and statistical significance will be considered for P

values less than 0.05. All statistical analyses will be performed using SPSS version 21 for windows (Chicago, ILL, USA).

9. Safety reporting

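### The protocol contradicts itself on when the carotid and femoral B-mode scan is done, and the secondary endpoint of change in IMT and echogenicity depends on that scan

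*Protocol*

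**What the plan says.** The synopsis lists as a secondary endpoint "Changes in subclinical atherosclerosis markers (carotid intima-media thickness and vascular wall and plaque echogenicity" (the bracket closes there). Section 6.2.3 shows where these quantities come from: IMT, plaque presence and the grey-scale median used for echogenicity are all read from the carotid and femoral B-mode examination.

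Four places bear on when that examination is done.

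- **Section 6.2.4, closing paragraph.** It first sets the vascular measurements at baseline and on the listed days of cycles 1 to 3. It then says "The B-Mode ultrasound of the carotid and femoral arteries will only be performed at baseline". The next sentence reads "On cycle 6 all vascular measurements will be repeated to assess the chronic effect of proteasome inhibition on vascular function and atherosclerosis".
- **Synopsis, description of study assessments.** "Vascular measurements include assessment of arterial stiffness, arterial wave reflections, subclinical carotid and femoral atherosclerosis and carotid plaque composition". The repeat schedule is "These measurements will be repeated on days 8,9,15 and 16 of cycle 1, on days 1,2 of cycles 2 and 3", and then "days 1,2,15 and 16 of cycle 6 or earlier if the patient develops progression of disease".
- **Section 4.1, part A.** IMT, plaques and echogenicity are listed under vascular structure, and "long term changes in vascular structure after treatment will be assessed".
- **Section 7, schedule table.** A single row for vascular studies is marked through to the column headed "C6d1or 6 months after baseline". There is no separate line for B-mode.

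**The concern.** A change endpoint needs a baseline value and at least one later value from the same examination. The one sentence that deals specifically with B-mode limits it to baseline. A sonographer or site coordinator following the explicit word *only* would have good reason to skip the scan at cycle 6, and a scan not taken then cannot be recovered.

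At stake are the secondary endpoint on IMT and echogenicity and the part of Section 4.1 that promises long-term structural change. The opposite error is also possible: a site working from the synopsis would repeat the scan at interim visits where Section 6.2.4 does not want it.

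**Working it through.** No arithmetic underlies the plan's statement, so the check is to set the texts side by side and count the follow-up scans that each reading yields.

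| Reading | Source | Post-baseline B-mode scans | Change computable? |
|---|---|---|---|
| (a) Baseline only | Section 6.2.4, the B-mode sentence taken alone | 0 | No |
| (b) Baseline and cycle 6 | Section 6.2.4, the B-mode sentence together with the one after it | 1 | Yes, baseline to cycle 6 |
| (c) Every vascular visit | Synopsis as written | Repeats in cycles 1, 2, 3 and 6 | Yes, at several times |

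**Step 1: which reading of Section 6.2.4 is most natural?** The paragraph runs in three sentences: all measurements from baseline through cycle 3, then B-mode only at baseline, then all vascular measurements again at cycle 6. Read in order, the second sentence exempts B-mode from the interim repeats and the third brings everything back at cycle 6. The third sentence names atherosclerosis as a purpose. Section 4.1 and the cycle 6 mark in the Section 7 table agree with this. Reading (b) is therefore the likely intent, although the word *only* literally contradicts it.

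**Step 2: does reading (b) remove the conflict?** No. The synopsis repeats its vascular measurements on 4 later days of cycle 1 (8, 9, 15, 16), on 2 + 2 = 4 days of cycles 2 and 3, and on 4 days of cycle 6 (1, 2, 15, 16), which is 4 + 4 + 4 = 12 days. It includes the carotid and femoral measures without exception. Under (b), Section 6.2.4 has none of the 8 interim scans (4 in cycle 1, 4 in cycles 2 and 3). The two texts disagree whether (a) or (b) is adopted.

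**Step 3: can the schedule table decide?** No. One row covers all vascular studies and is marked at interim visits as well as at cycle 6. Taken at face value it supports (c), but it cannot show an exception for one component. Cardiac ultrasound, by contrast, has its own row and a plain statement in Section 6.3 that it is done at baseline and at 6 months.

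**Step 4: what does (b) leave open?** The endpoint would rest on two occasions, so the repeated-measures analysis in Section 8 reduces to a two-time-point comparison for these variables. The visit that carries the scan is not fixed either. The synopsis gives four days in cycle 6, or earlier on progression. The table gives cycle 6 day 1 or 6 months. With the 28-day cycle of Section 6.1.2, cycle 6 day 1 falls 5 × 28 = 140 days after cycle 1 day 1, which is short of 6 months.

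**The case against.** The strongest reply is that nothing is lost. Section 6.2.4 read as a whole already yields a cycle 6 scan, and every other statement on follow-up of vascular structure supports a later scan. Only one loosely worded sentence, taken out of its paragraph, suggests otherwise. That argument stands as far as the likely intent goes, and it limits the finding.

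Two stronger inferences are tempting, and the documents do not support them.

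- A reader might conclude that the endpoint cannot be computed, so that none of the 46 planned patients would have a change value. That follows only if the sentence on cycle 6 is ignored. It is the worst case under the less plausible reading, not an established consequence.
- A reader might conclude that the primary objective on atheromatosis cannot be answered. The primary endpoints in the synopsis are haemodynamic markers and peripheral vascular function, and none of them needs B-mode. The ankle brachial index, which Section 6.2.4 describes as a surrogate for atherosclerosis, is not limited to baseline. Nor is arterial stiffness, which Section 4.1 lists under structure.

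The reply does not dispose of the mismatch with the synopsis, which remains under the favourable reading. Nor does it protect against an operator who follows the explicit restriction.

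**Conclusion.** Wrong as written: an internal inconsistency in the B-mode schedule. It lies within Section 6.2.4, and between that section and the synopsis, and the Section 7 table cannot resolve it.

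The consequence depends on the reading followed. With the baseline-only sentence taken literally, the secondary endpoint on carotid IMT and wall and plaque echogenicity has no follow-up value. On the likely intended reading it has one follow-up value, at cycle 6, and the change can be calculated. The primary endpoints are unaffected.

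This rests on two points: that IMT, plaque and grey-scale median come only from the B-mode examination, as Section 6.2.3 describes, and that no document outside the protocol fixes the scan dates. The point merits correction before enrolment because a missed scan is irrecoverable and the correction is cheap.

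**What to change.** 1. In Section 6.2.4, replace the B-mode sentence with wording such as: *Carotid and femoral B-mode scanning is done at baseline and repeated once, at cycle 6 (or at 6 months from baseline, or sooner on disease progression), and not at the interim visits.* The two alternatives in brackets must stay. Both are already in the protocol (table and synopsis). Because Section 5.4.1 makes progression a reason for discontinuation, a rule tied to cycle 6 alone could lose the follow-up scan in patients who progress early.
2. In the synopsis, except B-mode from the interim repeats.
3. In the Section 7 table, give B-mode its own row, marked at baseline and in the column for cycle 6 day 1 or 6 months.

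The cost is a wording change and at most one repeat scan per patient, or up to 46 × 1 = 46 scans, at a visit that already takes place. If reading (b) was always intended, no scans are added.

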6.3 Cardiac Ultrasonography

Study participants will undergo a baseline echocardiographic examination before the initiation of the treatment. Standard protocol will be used and standard measurements from 2-D and Doppler echocardiography will be made. LV end-diastolic and end-systolic volumes, as well as ejection fraction will be derived from the apical 4- and 2-chamber views using the biplane Simpson's rule. Left ventricular mass will be calculated according to Devereux's formula.

Doppler examination will include interrogation of mitral inflow, and early (E) and late (A) peak diastolic velocities and deceleration time will be measured. Tissue Doppler analysis will include pulse wave interrogation of the medial and lateral mitral annulus, peak diastolic early E' annular velocities will be obtained and the mean value and E/E' will be calculated. In addition, Speckle-tracking analysis will be applied to estimate LV rotational mechanics, and longitudinal strain parameters. Parasternal short-axis views at the level of the mitral valve and apex, and standard apical views (4-, 2-, 3-chamber) will be recorded for each study participant, according to the recommendations of the European and American Societies of Echocardiography. Five consecutive beats in each view will be stored digitally for off-line analysis. The frame rate will be set at between 50-100 frames/s, the sector width will be set as narrow as possible, and gain settings optimized. Global longitudinal strain and left ventricular twist will be assessed. Evaluation of cardiac function will be performed at baseline and thereafter at 6 months or earlier if a suspicious event occurs necessitating evaluation of cardiac function.

6.4 Study of Proteasome activity

In order to examine the molecular and cellular effects of therapeutic inhibitors in blood cells of MM patients, we will proceed to isolation of Red Blood Cells (RBCs) and Peripheral Blood Mononuclear Cells (PBMCs); these two cell types represent either a non-nucleate relatively "long-lived" proteome (RBCs) or cell lineages with the capacity to mobilize genome responses after proteasome inhibition (PBMCs). The blood samples which will be used in this research will be collected between specific time points of therapeutic proteasomal inhibitors administration. The first day of the treatment (no drug administration) will be used as a control time point.

Blood collection – isolation of cells

PBMCs and RBCs will be collected from whole blood of MM patients by using Ficoll-Paque (density 1.077 ± 0.001 g/mL at 20°C). Specifically, freshly collected heparinized blood will be transferred from each blood collection tube into a 15 mL tube. Blood will be diluted with phosphate-buffered saline [(PBS) 1:1 dilution]. The diluted blood will be carefully layered over the separation medium (2:1) and the two phases will be kept separated before the centrifugation. Subsequently, the tubes will be centrifuged at 400 xg for 30 min, at 20°C, acceleration 9, no brake (braking rate 0). Both cell types will be collected and washed with PBS.

RNA extraction and Quantitative Real-Time PCR (Q-RT-PCR) analyses

Total RNA will be extracted from selected patients PBMCs and will be quantified with BioSpec-nano spectrophotometer (Shimadzu Inc.). RNA (100 ng) will be then converted to cDNA, and Real-time PCR expression analyses of proteasomal genes, as well as of genes involved in cell proteostatic (e.g. autophagy or chaperones) or antioxidant modules, will be

performed using appropriate master mix and the PikoReal 96 Real-Time PCR System. Specific primers will be designed using the primer BLAST tool (http://www.ncbi.nlm.nih.gov/tools/primer-blast/) (35).

Measurement of proteasome peptidase activities in PBMCs and RBCs extracts

For measuring proteasome peptidase activities, blood cells will be lysed on ice by using a buffer suitable for the isolation of 26S proteasome (35-36) and lysates will be centrifuged at 19.000 xg (4 °C). Cleared lysates will be then adjusted with the Bradford method and the proteasome CT-L (LLVY) or C-L (LLE) peptidase activities will be measured by recording (excitation, 350 nm; emission, 440 nm) the hydrolysis of the fluorogenic peptides Suc-Leu-Leu-Val-Tyr-AMC, Z-Leu-Leu-Glu-AMC (35).

Preparation of cell protein extracts, immunoblotting analyses and detection of protein carbonyl groups

Total proteins (from RBCs or PBMCs) will be extracted using a buffer containing 150 mMNaCl, 1% Nonidet P-40, 0.1 % SDS, 50 mMTris–HCl, pH 8.0. Cell lysate of each sample will be centrifuged for 10 min at 19,000 xg (4 °C). The protein content will be adjusted with the Bradford method and will be then analyzed by SDS-PAGE and immunoblotting [e.g. of total proteome ubiquitination (ubiquitin conjugates) or proteasomal subunits) will be performed as previously described (37). Primary and horseradish peroxidase-conjugated secondary antibodies will be incubated for 1 h at RT. Immunoblots will be developed by an enhanced chemiluminescence reagent kit. Analysis of blots quantification will be performed by scanning densitometry(38).

For the detection of proteome carbonylation (or detection of oxidized proteins) in cell extracts the OxyBlot protein oxidation detection kit (Millipore, Billerica, MA; #s7150) will be used, as per manufacturer's instruction (37-38).

Confocal microscopy

Isolated PBMCs from selected patients will be fixed in 4% formaldehyde in PBS. They will then be transferred into poly-L-lysine coated slides and be permeabilized with 0.1% TritonX-100 as previously described with minor modifications (39). Blocked cells (1% BSA in PBS) will be incubated with primary anti-Ub antibodies (or antibodies against other cellular targets) and appropriate secondary antibody for 1 h at RT. For visualizing nuclei cells will be counterstained with DAPI. Samples will be imaged using a Nikon EZ-C1 confocal microscope equipped with a Nikon Plan APO 60.0×/1.40 oil immersion objective(40).

Measurement of Reactive Oxygen Species (ROS)

For the assessment of ROS production, cells will be incubated with 10 μ M CM-H₂DCFDA dye (ThermoFisher Scientific) in PBS for 30 min at 37°C in the dark (35). Following dye removal, cells will be incubated for 10 min with PBS and then, will either be stained with DAPI and viewed at the NIKON C1 CLSM or the produced fluorescence will be measured using the Infinite 200 Tecan microtiter-plate photometer (Tecan Trading AG, Switzerland) at excitation and emission wavelengths of 490 and 520 nm, respectively.

